## 9.2 STUDY PROCEDURE

### A. *Pre-procedure Preparation*

Just prior to and/or during the procedure, a glycoprotein IIb/IIIa inhibitor or other platelet inhibitor may be administered if it is standard practice. If the FIRMap catheter is to be used, heparin should be administered prior to insertion per local protocol in order to achieve and maintain ACT > 300. Heparin should be administered immediately following transeptal puncture in the case that ACT is not >300.

### B. *Intra-procedure Guidelines*

During the procedure, the following actions should be taken and appropriate data collected. Table 6.

**Table 5 – Intra-Procedure Guidelines**

Parameter	Description
-----------	-------------

Vascular access	Under sterile technique, the right and/or left femoral veins may be cannulated via Seldinger, or percutaneous approach. Other vascular access also may be obtained based upon physician judgment.
Reference catheter placement	Reference catheters (including 64-pole FIRMap catheter(s)) may be inserted and placed within the heart to record signals as clinically required at the discretion of the physician.
Access to left atrium	Access to the left atrium should be made according to the institution's standard practice.
Anticoagulation	Heparin should be administered per local protocol in order to achieve and maintain ACT > 300 prior to insertion of FIRMap catheter, if applicable. Heparin should be administered immediately following transeptal puncture in the case that ACT is not >300.
Catheter placement	Catheters may be inserted and used according to the institution's standard practice.
Source arrhythmia diagnosis	For FIRMap patients only: After obtaining at least 1 minute of continuous electrograms from the 64-pole FIRMap catheter either simultaneously or sequentially in the right and left atria, these electrogram data will be transferred to the RhythmView system. Right atrial mapping will initially be performed. If no right atrial rotor/source is detected or all right atrial rotors are eliminated, left atrial mapping will be performed. This will then produce FIRMap displays which will be interpreted by the operator to determine which locations have focal or rotor rhythms that could be sources of the AF.
3-D Electroanatomic Mapping	3-D electroanatomic maps may be created using CARTO (Biosense Webster, Johnson & Johnson) or Nav-X (St. Jude Medical) systems for documentation of anatomy and ablation lesion locations.
Induction of sustained AF	If the patient is not experiencing spontaneous, sustained AF (>5 min uninterrupted), induce sustained AF by atrial burst pacing from a catheter positioned within the CS or left atrial appendage until the atrial refractory period is reached or AF is induced with or without isoproterenol infusion.  IF AF CANNOT BE SUSTAINED, THE PATIENT DOES NOT MEET THE INCLUSION CRITERIA FOR THE PROTOCOL AND THE PATIENT WILL UNDERGO CONVENTIONAL AF ABLATION PER PHYSICIAN DISCRETION.
Ablation data	For each ablation, the following data will be recorded: time, catheter size, lesion number, duration of application, average and maximum temperature.

FIRM-guided procedure	Under fluoroscopic guidance, a cardiac ablation catheter is passed to the location(s) identified as AF source rhythms (rotors or focal impulses). FIRM-guided ablation is performed at sites identified by the initial or repeated FIRMap. Such ablation typically consists of 3-5 minutes of ablation in the rotor core region followed by repeat mapping to confirm that the rotor has been eliminated. Following each FIRM guided site ablation, FIRMap is repeated and is followed by rotor ablation until all rotors are eliminated or AF terminates and remains noninducible. If AF terminates and is noninducible prior to repeat mapping, ablation of any identified and targeted rotor core region should be completed fully (e.g. ablation of the anatomic region with 3D electroanatomic guidance). In this FIRM-guided ablation arm, no PV isolation is performed. In case a rotor is located inside the PVs, focal ablation of the rotor (but no PVI) can be performed if the risk for PV stenosis is considered to be minimal as per discretion of the operator.
Conventional Ablation	Conventional ablation consists of isolation of all four pulmonary veins with confirmed entrance block assessed by a multipolar catheter.
Additional ablation for other arrhythmias (non-AF)	Additional ablation for other arrhythmias will be noted for atrial tachycardia (AT) and/or right cavo-tricuspid isthmus ablation in the event that the patient has documented AT/atrial flutter prior to or during the procedure.
ACT values	Activated Clotting Times (ACT) value is first measured prior to insertion of FIRMap catheter or trans-septal puncture, whichever comes first, to determine baseline value and then every 30 minutes post-heparinization until therapeutic and, subsequently, every 30 minutes during left-atrial access. (Heparin dosage should be adjusted to maintain ACT above 300 sec). The ACT will be monitored every 30 minutes following initial heparin delivery until the target value is achieved and subsequently checked at least every thirty minutes during the procedure.
Vascular access sheath removal	The vascular access sheaths will be removed according to the institutional standard.

**The following precautions should be taken per standard of practice:**

- Typically, in order to reduce the risk of introducing air emboli through a transseptal sheath into the left atrium, the following precautions are taken:

- Aspiration or spontaneous bleed back from the trans-septal sheath side-port may be performed after each catheter withdrawal
- Trans-septal catheter insertion and withdrawal will always be performed slowly
- Unnecessary catheter exchanges may be avoided
- The time any trans-septal sheath is through the septum may be minimized
- The time multiple sheaths cross the septum may be minimized.
- Just prior to ablation, at each ablation site close to the right superior PV or in the posterior RA, pacing at high output (>15 mA) from the ablation catheter tip or fluoroscopic visualization of diaphragmatic movement may be used to assess whether the phrenic nerve is in proximity to the ablation zone. These data will be documented and used to guide ablation at each site.
- Esophageal temperature monitoring during ablation in the posterior LA, per local standard of care, may also be considered.

### C. *Intra-procedure Measurements*

The following data will be collected during the procedure. Table 6.

Data	Description
Fluoroscopy times	To be recorded: Total fluoroscopy time 
 
● The total fluoroscopy time for the procedure (a.k.a., "pedal down" time)
 

Total RF ablation time	Total RF ablation time as measured by total time of ablation lesion applications, from first ablation lesion to end of last lesion, will be documented. These values will be noted in both the FIRM-guided and conventional ablation groups. If ablation for AT/atrial flutter is pursued, this ablation time will be documented separately
Total procedure time	Total procedure time defined as: time from insertion of first sheaths for vascular access to removal of sheaths.
Medication administration	Cardiac medications administered during the procedure including drug name, dosage, and indication and will be recorded.
Devices and equipment	Devices and equipment used during the procedure including access devices, diagnostic and ablation catheters, and mapping equipment type will be recorded.

#### D. *Post-procedure & Discharge Requirements*

The measurements and evaluations that will occur at post-procedure are provided below.

- Post-ablation and following recovery from anesthesia, subjects will be monitored until stable.
- Post-procedure OAC will be performed according to the institutional standard and the most recent international guideline recommendations.
- Post-procedure drug therapy will include re-initiation and/or continuation of any pre-procedure cardiac medications. Administration of anti-arrhythmic drugs is allowed in the first three months post procedure only. Supplemental anti-arrhythmic medications will be administered under the direction of the investigator and documented in the appropriate section(s) of the case report forms.
- Post procedure rhythm monitoring will occur via a 72-hour ambulatory continuous ECG monitor (Holter) or a Cardiac Implanted Electronic Device (CIED). CIED recordings will be censured for only noting events during the 72 hours preceding the 3, 6, and 12-month follow-up evaluations.
- Pre-discharge evaluation will include:
  - Diagnostic 12-lead ECG
  - Symptom and rhythm assessment
  - Antiarrhythmic medications
  - Adverse event documentation and treatment, as necessary.

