**Table 1 – Primary Effectiveness Endpoint**

Endpoint	Definition
Long term success	
Single-procedure freedom from AF/AT recurrence from 3-12 months post index ablation procedure (with 90-day blanking period).
 
* Freedom from AF/AT recurrence is defined as no documented episodes of AF/AT > 30 seconds with conventional non-invasive monitoring. In the case of a cardiac implanted electronic device (CIED), freedom from AF recurrence is defined as no documented episodes of AF/AT > 30 seconds in a 72-hour window at the follow-up visits in addition to any symptomatic episodes with documented AF > 30 seconds. AT recurrence does not include episodes of CTI (cavotricuspid isthmus) dependent flutter.

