**Table 7 Follow-up (FU) Visit Windows**

Visit	Allowed Visit Date Range
Day 7 to 10 days (Phone or visit)	N/A
3 months (90 days)	± 2 weeks
6 months (180 days)	± 2 weeks
12 months (360 days)	± 4 weeks

- ***Resolution Period***

Following ablation treatment, subjects will undergo a 90-day “resolution” period (aka “blanking period”) where medical therapy may be optimized and where any of the procedurally-derived arrhythmias that commonly follow ablation procedures may resolve. During this period, adverse events will be accumulated but primary efficacy measurements will not be performed. In case of repeat ablation is solely for treatment of common type (cavo-tricuspid isthmus dependent) flutter, the patient has not failed the primary long-term efficacy endpoint.

*Note: During the 90-day resolution period, medications may be adjusted as medically indicated, and as indicated in above section. Any clinically indicated changes must be documented along with the reason for change.*

- ***Anti-arrhythmic Medications***

Anti-arrhythmic medications can be discontinued anytime from Day 91 to Day 180 post-procedure. The date of discontinuation will be determined by each investigator on a patient-by-patient basis, but must occur sometime from Day 91 to Day 180 post-procedure.

- ***Recurrence of AF***

If re-ablation for AF (not including common type atrial flutter) is necessary after documentation of the recurrent arrhythmia has

occurred, the patient will be considered a primary efficacy study failure but still followed up for AF burden.

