#### F. *Unscheduled Follow-up Visit*

The following assessments/procedures may include:

- Diagnostic 12-lead ECG
- 72-hr ambulatory continuous ECG monitor (Holter) or CIED interrogation 72 hours prior to visit, as applicable
- EQ-5D and AFEQT Quality of Life survey
- Symptom and rhythm assessment
- Concomitant anti-arrhythmic medications
- Adverse event documentation

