#### 1.2.1.4 Long Term Effectiveness (primary effectiveness endpoints)

Single-procedure freedom from AF recurrence from 3-12 months after the index AF ablation procedure (with 90-day blanking period).

\*Freedom from AF recurrence is defined as no documented episodes of AF > 30 seconds with conventional non-invasive monitoring. In the case of a cardiac implanted electronic device (CIED), freedom from AF recurrence is defined as no documented episodes of AF > 30 seconds in a 72-hour window at the follow-up visits in addition to any symptomatic episodes with documented AF > 30 seconds.

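### Protocol 9.2 D leaves unnoted some device-only symptomatic AF that Table 1 and SAP 1.2.1.4 count as primary failure, and the endpoint's AF/AT wording is inconsistent

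*Protocol*

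**What the plan says.** Four places bear on how a CIED subject is classified.

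- **Protocol 9.2 D**, on monitoring after the procedure: "CIED recordings will be censured for only noting events during the 72 hours preceding the 3, 6, and 12-month follow-up evaluations". It makes no exception for symptoms.
- **Protocol Table 1**, the primary endpoint. The first ground for failure is breach of "no documented episodes of AF/AT > 30 seconds in a 72-hour window at the follow-up visits". The second is given by "in addition to any symptomatic episodes with documented AF" lasting more than 30 seconds. The second ground has no time window and names no source of documentation. Table 1 also excludes CTI-dependent flutter from AT recurrence.
- **SAP 1.2.1.4** repeats the two grounds, "in a 72-hour window at the follow-up visits in addition to any symptomatic episodes with documented AF > 30 seconds", but names AF alone in every part and does not mention the flutter exclusion. SAP 2.2.1 and Protocol 15.2 A name AF/AT in their statements of the primary endpoint.
- **Protocol 9.3 F**, unscheduled visits, lists as a possible assessment "72-hr ambulatory continuous ECG monitor (Holter) or CIED interrogation 72 hours prior to visit, as applicable".

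Neither document says which rule governs where they differ.

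**The concern.** Table 1 defines the endpoint, and 9.2 D tells sites what to take from the device. If the collection rule is narrower than the definition, some events that make a subject a failure may never reach the case report form, and the independent committee that adjudicates endpoint events (Protocol 12.5) can only judge what is reported. Site staff know the treatment arm: Protocol section 5 blinds subjects only, and SAP 1.1.6 says there is no masking. Staff who know the arm should not have two rules to choose between.

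The word 'only' in 9.2 D would also exclude device readings taken at unscheduled visits, which 9.3 F allows. It affects the secondary endpoint of AF recurrence from 0 to 12 months without blanking as well, because nothing on the device before the 3-month window would be noted.

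The AF/AT wording is a related defect in the same definition. As Table 1 stands, AT seen on a CIED counts inside the windows, but symptomatic AT outside them does not count under the CIED clause. Under SAP 1.2.1.4 no AT counts at all.

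**Working it through.** **1. The plan's own figures.** Protocol 15.3 gives 77 per arm for 80% power, with success 0.50 (conventional) and 0.55 (FIRM), margin 0.15 and a one-sided 95% limit. The normal-approximation formula returns 77 per arm. Exact enumeration with the Newcombe-Wilson limit gives power 0.806. Adding 10% for drop-out gives 154 × 1.10 = 169.4, hence 170. These reproduce, and none depends on the CIED rule.

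**2. The rules side by side.** Take day 250. The latest 6-month visit is day 180 + 14 = 194. The earliest 12-month visit is day 360 − 28 = 332, so its window opens about day 329. Day 250 is outside every window.

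| Event in a CIED subject (> 30 seconds) | Table 1 | SAP 1.2.1.4 | 9.2 D |
|---|---|---|---|
| AF in the 72 hours before the 6-month visit | failure | failure | noted |
| Asymptomatic AF, day 250, device only | not counted | not counted | not noted |
| **Symptomatic AF, day 250, device only, no re-ablation** | **failure** | **failure** | **not noted** |
| Symptomatic AF, day 250, also on ECG | failure | failure | ECG not restricted |
| AT (not CTI-dependent flutter) in the 72 hours before the 6-month visit | failure | not counted | noted |
| Symptomatic AT, day 250, device only | not counted by the CIED clause | not counted | not noted |

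The third row is the conflict between 9.2 D and the endpoint. The last two rows show the AF/AT inconsistency.

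Re-ablation matters because Protocol 9.3 makes re-ablation for AF after a documented recurrence a primary failure in its own right.

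**3. Windows as a share of the endpoint period.** Day 91 to day 360 is 270 days.

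- Three windows: 3 × 3 / 270 = 9/270 = 3.3%.
- With the 3-month visit on its nominal day 90, that window lies in the blanking period, when "During this period, adverse events will be accumulated but primary efficacy measurements will not be performed". This leaves 6/270 = 2.2%.

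These are shares of time. They do not measure the disputed events, because Table 1 also ignores asymptomatic device events outside the windows.

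**4. Size per subject.** One reclassified subject moves an arm's crude success proportion by 1/85 = 1.2 points (1/77 = 1.3 points), against a 15-point margin. The number of CIED subjects is not given. As an assumed range, 1, 2, 4 or 8 subjects reclassified in one arm of 85 give 1.2, 2.4, 4.7 or 9.4 points.

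**5. Direction.** With k_C and k_F unnoted failures in the conventional and FIRM arms of 85, δ = p_C − p_F changes by (k_C − k_F)/85. This has either sign and is zero when the counts are equal. If instead the same fraction f of failures is missed in each arm, the observed difference is δ(1 − f). At the plan's δ = 0.50 − 0.55 = −0.05 this moves toward zero, slightly against FIRM. At δ = +0.15 it moves toward zero in favour of non-inferiority. The documents do not settle which applies.

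**The case against.** The strongest reply is that 9.2 D restricts device recordings and nothing else. Table 1's symptomatic clause does not require the device as its source. Symptoms and rhythm are assessed at every scheduled visit, a 12-lead ECG may be taken at an unscheduled one, and re-ablation for recurrent AF is a failure anyway. Most symptomatic recurrences therefore have another route into the endpoint. This stands, and it confines the point to the third row of the table.

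A reader might infer more in four ways, and the documents do not support any of them.

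- *That 9.2 D discards 96.7% of endpoint-relevant device data.* Most of that time is left out by Table 1 too. Only symptomatic episodes within it are in dispute, and their number is unknown.
- *That 9.2 D makes detection differ between CIED and Holter subjects.* Limiting the device to 72 hours before each visit matches the scheduled 72-hour Holter. It is Table 1's symptomatic clause that may give CIED subjects more capture.
- *That missed failures bias the trial toward non-inferiority.* Step 5 shows that the sign depends on the true difference and on any imbalance.
- *That the endpoint could never be recovered.* The case report forms and the retention of device data are not described, so recovery can be neither shown nor excluded.

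One could also read 9.2 D as describing scheduled monitoring only. That may be what was meant, but the sentence says 'only' and does not refer to Table 1.

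**Conclusion.** The point holds in this limited form. The recording rule in Protocol 9.2 D is narrower than the primary endpoint in Table 1 and SAP 1.2.1.4. A CIED subject with symptomatic AF outside the windows, documented by the device alone and without re-ablation for AF, is a failure under the definition, but the episode would not be noted under 9.2 D. The AF-only wording of Table 1's symptomatic clause and of SAP 1.2.1.4 is a second inconsistency with the AF/AT endpoint.

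The likely effect is small. This rests on two things: permanent pacemakers are excluded (Protocol 7.1 B), so CIED subjects are probably few, and only device-only episodes are affected. The per-subject figure assumes crude proportions in arms of 85, whereas the plan estimates success by Kaplan-Meier. The sample size is unaffected, and no effect on the primary conclusion is shown.

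**What to change.** Reconcile Protocol 9.2 D, Table 1 and 9.3 F with SAP 1.2.1.4:

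1. In 9.2 D, have sites note CIED events in the 72-hour windows and, for the primary endpoint, any symptomatic device-documented episode after Day 90. State separately what is noted before Day 90 for the secondary endpoint without blanking.
2. State whether CIED interrogations at unscheduled visits count toward the endpoint.
3. Write AF/AT in the symptomatic clause of Table 1 and throughout the SAP 1.2.1.4 definition. Changing only the symptomatic clause of the SAP would count symptomatic AT but not AT in the windows, which is a new contradiction.
4. Keep Table 1's exclusion of CTI-dependent flutter, and carry it into SAP 1.2.1.4.

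The cost is wording in two documents, since devices are already interrogated at the 3-, 6- and 12-month visits. The downside is that symptomatic episodes will be captured more completely in CIED than in Holter subjects, who have no continuous recorder between visits. Table 1 already accepts that difference.

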### 9.3 FOLLOW-UP REQUIREMENTS

- ***Follow-Up Visit Schedule***

Each enrolled subject will return for visits with the electrophysiologist in accordance with Table 8 below. The day of the study procedure represents Day 0. Study visits that do not occur within the below time windows will be considered protocol deviations.

**Table 7 Follow-up (FU) Visit Windows**

Visit	Allowed Visit Date Range
Day 7 to 10 days (Phone or visit)	N/A
3 months (90 days)	± 2 weeks
6 months (180 days)	± 2 weeks
12 months (360 days)	± 4 weeks

- ***Resolution Period***

Following ablation treatment, subjects will undergo a 90-day “resolution” period (aka “blanking period”) where medical therapy may be optimized and where any of the procedurally-derived arrhythmias that commonly follow ablation procedures may resolve. During this period, adverse events will be accumulated but primary efficacy measurements will not be performed. In case of repeat ablation is solely for treatment of common type (cavo-tricuspid isthmus dependent) flutter, the patient has not failed the primary long-term efficacy endpoint.

*Note: During the 90-day resolution period, medications may be adjusted as medically indicated, and as indicated in above section. Any clinically indicated changes must be documented along with the reason for change.*

- ***Anti-arrhythmic Medications***

Anti-arrhythmic medications can be discontinued anytime from Day 91 to Day 180 post-procedure. The date of discontinuation will be determined by each investigator on a patient-by-patient basis, but must occur sometime from Day 91 to Day 180 post-procedure.

- ***Recurrence of AF***

If re-ablation for AF (not including common type atrial flutter) is necessary after documentation of the recurrent arrhythmia has

occurred, the patient will be considered a primary efficacy study failure but still followed up for AF burden.

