**B. Three-Month Follow-up ( $\pm$  2 weeks)**

The following assessments/procedures will be performed:

- Diagnostic 12-lead ECG
- 72-hr ambulatory continuous ECG monitor (Holter) or CIED interrogation 72 hours prior to visit, as applicable
- EQ-5D and AFEQT Quality of Life survey
- Symptom and rhythm assessment
- Concomitant anti-arrhythmic medications
- Adverse event documentation

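### On 15 of the 29 permitted days the 3-month recording falls inside the blanking period and cannot count, so subjects have two or three countable recordings depending on visit date

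*Protocol*

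**What the plan says.** The primary endpoint in Protocol Table 1 is "Single-procedure freedom from AF/AT recurrence from 3-12 months post index ablation procedure (with 90-day blanking period"). Days are counted from the ablation: "The day of the study procedure represents Day 0" (Protocol 9.3). Table 7 puts the 3-month visit at 90 days with a two-week allowance either side, the 6-month visit at 180 days with the same allowance, and the 12-month visit at 360 days with four weeks either side.

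The Resolution Period text under Table 7 defines a 90-day blanking period and states that in it "adverse events will be accumulated but primary efficacy measurements will not be performed". Section 9.3 B nevertheless requires, at the 3-month visit, a "72-hr ambulatory continuous ECG monitor (Holter) or CIED interrogation 72 hours prior to visit, as applicable". For implanted devices, section 9.2 D adds that "CIED recordings will be censured for only noting events during the 72 hours preceding the 3, 6, and 12-month follow-up evaluations".

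Neither document says whether a 3-month recording made on or before Day 90 is counted, repeated or ignored. SAP 2.2.1 restates the endpoint and the 90-day blanking but gives no rule on which recordings enter it. On blinding, Protocol section 5 covers subjects only, and SAP 1.1.6 says there is no masking at all.

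**The concern.** The visit window straddles the end of blanking. A site that follows Table 7 exactly can produce a 3-month recording that the blanking text excludes from the primary endpoint. Only three recordings are scheduled, so the loss of one is not trivial.

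Two things follow. First, ascertainment is uneven: some subjects are examined three times in the efficacy period and others twice, for no reason other than the visit date. Second, average detection falls. Subjects whose recurrence is missed are counted as free of it, which pulls the two arms together. In a superiority trial that costs power. In a non-inferiority trial it makes a truly worse treatment look closer to its comparator, so the error lies on the side that matters. If the visit date were also related to treatment arm, a further bias would be added, in whichever direction the imbalance ran.

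**Working it through.** **1. The plan's own figure.** Protocol 15.3 gives 77 per arm for 80% power at 0.50 (conventional) and 0.55 (FIRM), margin 0.15, with a one-sided 95% Newcombe-Wilson interval. Exact enumeration of that interval at 77 per arm gives 80.6%, so the figure reproduces. The analysis rule in Protocol 15.2 A and SAP 2.2.1 uses a two-sided 95% interval, so steps 4 and 5 use that.

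**2. Days (Table 7, Day 0 = procedure).**
- 3-month visit: 90 − 14 = Day 76 to 90 + 14 = Day 104, which is 29 permitted days.
- Inside blanking: Day 76 to 90, 15 days, including the nominal day. After blanking: Day 91 to 104, 14 days.
- CIED look-back of 72 hours: wholly on or after Day 91 only if visit day − 3 ≥ 91, so Day 94 to 104, 11 days. Visits on Day 91 to 93 give a partial recording.
- 6-month visit: Day 166 to 194. 12-month visit: Day 332 to 388. Both always fall after blanking.

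The count of 15 takes the recording as complete by the visit. The documents do not say whether a Holter is fitted or returned at the visit. If fitted then, one started on Day 88 to 90 would run partly past Day 90, leaving 15 − 3 = 12 days wholly inside blanking.

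**3. Scheduled recording time.** Three recordings: 3 × 72 = 216 h. Two: 2 × 72 = 144 h. Loss: 72/216 = 33% of scheduled hours.

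**4. Illustration of the effect on the test.** Per-recording detection, q, is not in the documents, so a range is used. Assumptions: independent recordings with equal q; no other route of detection; visits spread evenly over the 29 days in both arms; true freedom 0.50 (conventional) and 0.35 (FIRM), exactly at the margin; 85 per arm, all evaluable; simple proportions; non-inferiority declared when the lower two-sided 95% Newcombe limit for FIRM minus conventional exceeds −0.15.

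- Detection with three recordings: D3 = 1 − (1 − q)³. With two: D2 = 1 − (1 − q)².
- Window as written: Dw = (15/29) × D2 + (14/29) × D3.
- Observed freedom: 1 − 0.50 × D and 1 − 0.65 × D. Observed deficit: 0.15 × D.

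Example, q = 0.40: D3 = 0.784, D2 = 0.640, Dw = 0.331 + 0.378 = 0.710 (from unrounded terms). The observed deficit is 11.8 points with three recordings and 10.6 points under the window as written.

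| q | D3 | D2 | Dw | P(declare NI), all three count | P(declare NI), window as written |
|---|---|---|---|---|---|
| 30% | 0.657 | 0.510 | 0.581 | 10.9% | 14.8% |
| 40% | 0.784 | 0.640 | 0.710 | 7.1% | 9.1% |
| 50% | 0.875 | 0.750 | 0.810 | 5.0% | 6.4% |
| 70% | 0.973 | 0.910 | 0.940 | 3.2% | 3.8% |

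Only the gap between the last two columns belongs to this point. The column with all three counting already exceeds the nominal 2.5% because intermittent monitoring misses recurrences whatever the visit window.

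**5. Alternative reading of the rates.** The endpoint is documented recurrence, so 0.50 and 0.35 may instead be taken as the rates seen with three countable recordings. The starting value is then 2.8%. Recurrence in each arm is multiplied by Dw/D3, which is 0.884 at q = 30% and 0.967 at q = 70%. The chance of declaring non-inferiority rises to 4.8% and 3.3% respectively.

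**The case against.** Several points on the other side are fair.

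- **Other routes of detection.** Table 4 requires 12-lead ECGs at the 6- and 12-month visits, unscheduled visits may include an ECG and a Holter, documented symptomatic episodes count under Table 1, and re-ablation for AF counts as failure under section 9.3. The 33% is a share of scheduled hours, not of endpoint detection. This stands, and makes the effect smaller than the illustration.
- **Dependence between recordings.** A subject with frequent AF will probably be caught at 6 or 12 months anyway, so the lost recording costs less than independence implies. A recording just after Day 90 may also be less sensitive if anti-arrhythmic drugs are still being taken; sections 9.2 D and 9.3 differ on how long they may be. This also stands.
- **Size.** A reader might take the whole excess over 2.5% as the effect of the window, or assume that every subject loses a recording, which at 40% detection gives 11.6%. The documents support neither. The 7.1% would remain after the fix, and 11.6% needs every 3-month recording in both arms to fall on or before Day 90.
- **Intent.** A reader might infer that unblinded sites can steer visit dates to favour FIRM. The documents do not say who sets the date, and nothing shows that timing differs by arm. The opposite imbalance would bias against FIRM.

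None of this removes the conflict between the visit window and the blanking text. Endpoint adjudication by the Data Monitoring Committee (Protocol 12.5) cannot recover a recording made too early.

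**Conclusion.** The point holds as a design flaw of modest size that should be corrected. Table 7 and the Resolution Period text together mean that a compliant visit, even on the nominal day, can yield a recording that cannot contribute to the primary endpoint, and neither document resolves this. The result is uneven ascertainment and lower average detection, and lower detection favours non-inferiority.

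Under the assumptions of step 4, the window adds between 3.8 − 3.2 = 0.6 and 14.8 − 10.9 = 3.9 percentage points to the chance of a wrong non-inferiority claim, for detection per recording of 70% down to 30%. Under step 5 it adds between 3.3 − 2.8 = 0.5 and 4.8 − 2.8 = 2.0 points. These are illustrations that lean towards the upper end, since other detection routes are left out. The day counts rest on the documents alone; the error rates do not. A directional bias between arms is possible because staff are not blinded, but it is not shown.

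**What to change.** - In Protocol 9.3, schedule the 3-month endpoint recording to lie wholly on or after Day 91 for every subject, within the existing window that ends on Day 104. For CIED look-backs this means visits on Day 94 to 104.
- In SAP 2.2.1, state that only recordings made after Day 90 count towards the primary endpoint.
- In the SAP tables, report the number of countable recordings per subject by arm, so that any imbalance is visible.

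No visit is added, and the endpoint, margin and sample size stay as they are. The cost is a usable recording window of about 11 to 14 days instead of 29, so some more minor window deviations are likely.
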